11.2 Calendar

Procedures	Screening	Cycle 1					Cycles 2-4 ^f	End of Treatment	Long Term Follow Up (± 14 days) ^h				
	Day -28 to Day 1	Day 1 ⁱ	Day 8 (± 2)	Day 15 (± 2)	Day 22 (± 2)	Day 42 (-3)	Day 1	8 weeks ± 7 days after treatment completion	6 Months	12 Months	18 Months	24 Months	36 Months
Medical History	X												
Physical Exam	X	X					X	X	X	X	X	X	X
Vital Signs ^o	X	X	X	X	X		X	X	X	X	X	X	X
Height/Weight	X	X					X	X					
Concurrent Meds Assessment	X	X					X						
Baseline Symptom Assessment	X												
Adverse Event Evaluation		X	X	X	X	X	X	X					
Tumor Tissue	X												
Peripheral Blood Sample	X					X		X					
ECOG Status	X	X					X	X					
CBC w/ differential	X	X	X	X	X		X	X	X	X	X	X	X
PT/INR	X												
Serum Chemistry ^a	X	X		X			X	X	X	X	X	X	X
LDH	X	X					X ^j	X					
Uric acid and phosphorous	X	X											
Pregnancy Test	X ^g												
Urinalysis	X												
Hepatitis Panel	X												
HIV testing	X												
EBV PCR	X ^j				X ^k		X ^k	X ^k	X ^k			X ^k	
ECG	X												
CT Neck/Chest/Abdomen/Pelvis ^c	X ^b				X ^e		X ^e	X ^e	X ^e			X ^e	
PET Scan ^c	X						X						

Bone marrow biopsy/aspiration	X^m							Xⁿ					
Disease Response Assessment						X		X					
Acalabrutinib ^d		X					X						
Rituximab		X	X	X	X		X						
Survival/Disease Status									X	X	X	X	X

- a. Sodium, potassium, chloride, bicarbonate, BUN, creatinine, calcium, glucose, total protein, albumin, alkaline phosphatase, total bilirubin, SGOT [AST], SGPT [ALT]
- b. Neck CT can be omitted at baseline at the discretion of the investigator if there was no suspicion for involvement
- c. PET and diagnostic CT scan preferred, but PET alone is preferred, if unable to obtain both.
- d. Acalabrutinib given on days 1-28
- e. CT neck can be omitted if there was no baseline involvement
- f. For subject in a CR after cycle 1, rituximab will be administered on the same schedule as cycle 1 (see Table 2). For these patients, no other study assessment will be done on days 8, 15, and 22.
- g. Pregnancy test to be done within 72 hours of starting the study drug. This only applies to women of childbearing potential.
- h. Patients with disease progression only need to have survival follow-up and current lymphoma treatment captured (see section 11.1.2). Virtual visits may be used to capture applicable procedures during long-term follow up only if the patient is unable to follow up with the in person.
- i. Cycle 1 Day 1 pre-dose assessment do not need to be repeated if being done same day as screening. If the same assessments are being used for both screening and day 1, the data should be entered at screening in the database.
- j. EBV PCR at baseline if not done within 1 month of diagnosis
- k. EBV PCR if positive at baseline
- l. LDH to be done only on Cycle 2 Day 1 (does not apply to Cycle 3 or 4)
- m. This can be omitted at investigator's discretion, if there is low or no suspicion of involvement
- n. Bone marrow aspiration and biopsy if positive at baseline
- o. Blood pressure, pulse, respiratory rate and temperature

12.0 MEASUREMENT OF EFFECT

Response assessments will be evaluated based on Lugano Criteria (refer to Appendix 3). Patients who achieve a CR or PR after cycle 1 treatment will have a CT scan approximately 8 weeks after the end of study treatment. Please see section 11 for the schedule of the imaging studies. Patients will have pre-treatment and end of treatment FDG-PET and/or CT to monitor their response to treatment. For each patient, every effort will be made to use the same radiologic imaging that was obtained at screening to be used to assess response. Interim response will be assessed after cycle 1 using CT scans. During follow up patients will have CT scans done at 6, 12, and 24 months after the last cycle of therapy.

All patients will be evaluable for toxicity from the time of their first treatment with rituximab and acalabrutinib.

The following guidelines are to be used for establishing tumor measurements at baseline and for subsequent comparison:

- The six largest dominant nodes or extranodal masses must be identified at baseline.
- If there are 6 or fewer nodes and extranodal masses, all must be listed as dominant. If there are more than 6 involved nodes or extranodal masses, the 6 largest dominant nodes or extranodal masses should be selected according to the following features:
 - nodes should be clearly measurable in at least two perpendicular measurements
 - nodes should be from as disparate regions of the body as possible
- Measurements for all dominant nodes and extranodal masses will be reported at baseline. Measurements on non-dominant nodes are not required. The lymph nodes or extranodal masses selected for measurement should be measured in two perpendicular diameters, one of which is the longest perpendicular diameter. The lymph nodes should be measured in centimeters to the nearest one tenth of a centimeter (e.g. 2.0 cm, 2.1cm, 2.2 cm, etc.)

12.1 Definitions

12.1.1 Overall Response Rate

Overall response rate (ORR) is defined as all patients that achieve a CR or PR based on end of treatment scans, using the Lugano Criteria.

12.1.2 Complete Remission Rate

Complete response rate (CRR) is defined as all patients that achieve a CR based on end of treatment scans, using the Lugano Criteria.

12.1.3 Partial Remission Rate

Partial response rate (PRR) is defined as all patients that achieve a PR based on end of treatment scans, using the Lugano Criteria.

12.1.4 Duration of Response

Duration of response (DOR) is only measured in responders. DOR is defined as the time from documented response (CR or PR) to the time of confirmed disease progression or death due to any cause, whichever occurs first. Subjects who are still alive and free from progression at the time of data cutoff date, lost to follow-up, have discontinued study, or have initiated other non-protocol anti-tumor therapy (NPT) will be censored at the last tumor assessment when subjects are progression-free.

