6.5 Duration of Follow Up

End of Treatment Response Assessment: End of treatment scans and visit will be completed within 8 weeks (± 7 days) of treatment termination. Subjects with stable or progressive disease after Cycle 1 Day 36 scans will go directly onto LTFU.

If there is an adverse event related to study drug, the clinical course of each event will be followed until resolution, stabilization, or until it has been determined that the study treatment or participation is not the cause with a cut off of 24 months after completion of therapy.

Serious adverse events that are still ongoing at the end of the study period will necessitate follow-up to determine the final outcome. Any serious adverse event that occurs after the study period and is considered to be possibly related to the study treatment or study participation will be recorded and reported immediately.

Long-Term Follow Up

Each subject should be followed for a total of 3 years after study treatment has ended. Follow up visits will occur at 6, 12, 18, 24 and 36 months after completion of treatment. During this period, subjects will be followed via physical exam and laboratory analysis. CT scans will be repeated at 6, 12, and 24 months. If the patient is unable to follow up in person, virtual visits may be used to capture applicable procedures during long-term follow up only. Subjects who

experience disease progression are not required to come in for clinic follow up. Study team will make every effort to contact them via phone to obtain information specified in the protocol (see section 11.1.2).

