- PET and diagnostic CT of neck, chest, abdomen, and pelvis with IV and PO contrast for response assessment. Neck CT can be omitted if no involvement at baseline. If insurance only allows one type of scan, PET scan is preferred for end of treatment assessment.
- Disease response assessment

- Bone marrow aspiration and biopsy if positive at baseline
- Peripheral blood sample for correlative studies

Duration of Follow Up

After completion of the study treatment the subjects will be followed for a total of 3 years. The follow up visits will be done at 6, 12, 18, 24 and 36 months after the last cycle of therapy. There is a \pm 14 day window for these visits. If the patient is unable to follow up in person, virtual visits may be used to capture applicable procedures during long-term follow up only.

The follow up visits should include the following:

- Survival/Disease Status
- Physical Examination
- Vital signs
- CBC with differential
- Serum chemistry panel
- Diagnostic CT neck, chest, abdomen and pelvis scan with IV and PO contrast will be done at 6, 12 and 24 months if no disease progression. Neck CT can be omitted if no involvement at baseline
- Peripheral blood EBV PCR if positive at baseline will be done at 6, 12 and 24 months
- Current lymphoma treatment

Patients who have stable/progressive disease are not required to come in for clinical follow up. These patients can be contacted over the phone by the study personnel to obtain the following information

- Survival/Disease Status
- Current lymphoma treatment

Patients will be followed for toxicity until the End of Treatment Response Assessment study visit or until death, whichever occurs first. The clinical course of each event will be followed until resolution, stabilization, or until has been determined that the study treatment or participation is not the cause.

Serious adverse events (SAE) that are still ongoing at the end of the study period will necessitate follow-up to determine the final outcome. Any serious adverse event that occurs after the study period and is considered to be possibly related to the study treatment or study participation will be recorded and reported immediately.

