12.1.5 Progression Free Survival

Progression free survival (PFS) is defined as the time from first dose to documented disease progression, or death from any cause, whichever occurs first. Data for subjects who are still alive and free from progression at the time of data cutoff date, lost to follow-up, have discontinued the study, or have initiated NPT will be censored on last assessment (or, if no post-baseline tumor assessment, at the time of first dose plus 1 day).

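### DOR counts deaths and progressions without a time limit but censors event-free responders at their last scan, so after the final scheduled CT only patients who fail remain at risk; PFS shares the fault on one reading of its wording

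*Combined protocol and SAP*

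**What the plan says.** **DOR (Section 12.1.4).** The event is "confirmed disease progression or death due to any cause, whichever occurs first". A responder without an event "will be censored at the last tumor assessment when subjects are progression-free".

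**PFS (Section 12.1.5).** The event is "documented disease progression, or death from any cause, whichever occurs first". Event-free patients "will be censored on last assessment (or, if no post-baseline tumor assessment, at the time of first dose plus 1 day".

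**Length of follow-up (Section 6.5).** The total is three years from the end of treatment, and the timetable reads: "Follow up visits will occur at 6, 12, 18, 24 and 36 months after completion of treatment".

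**Imaging.** Section 6.5: "CT scans will be repeated at 6, 12, and 24 months". Section 11.1.2 agrees that follow-up CT "will be done at 6, 12 and 24 months if no disease progression", and Section 12.0 gives the same three time points. The month-36 visit has examination, laboratory tests and survival/disease status but no scan, and may be virtual.

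**Estimator (Section 14.7).** Kaplan-Meier for the survival endpoints. No rule truncates the curve or deals with events after the last scan.

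**A second DOR definition (Section 14.5).** DOR there ends at progressive disease; death is not named.

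**The concern.** Kaplan-Meier needs censoring that carries no information about the later outcome. Under Section 12.1.4, a responder who is alive and progression-free at the month-36 visit leaves the risk set at the month-24 scan. A responder who dies at month 30 stays in it until month 30. Once scanning has stopped, whether a patient is still at risk depends on whether that patient goes on to fail. More patients do not cure this.

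Between scheduled scans the effect is limited, because a patient who stays event-free is carried forward by the next scan. After the final scan there is no next scan, and a year of event follow-up remains.

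At stake are the tail of the DOR curve, any 36-month estimate read from it, and the median if the curve first crosses 0.5 there. PFS is exposed in the same way if its censoring date is also a scan date.

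**Working it through.** **The plan's own figures.** The documents give no figure for DOR or PFS, so there is none to reproduce. The primary design does reproduce: for at least 44 responses in 62, the exact binomial upper tail at 60% is 0.0492 and the power at 75% is 0.812, in line with Section 14.2. This point does not touch it.

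**Illustration (patient counts assumed; months counted from end of treatment).** 44 responders, which is the success threshold in Section 14.2. Of these, 14 have events before month 24 and 30 are event-free at the month-24 scan. Two of the 30 die, at months 28 and 33; the other 28 are progression-free at month 36. At each event the estimate is multiplied by (1 − 1/number at risk).

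| Month | Censored at last scan (Section 12.1.4) | Kept at risk to month 36 |
|---|---|---|
| 24 | 30/44 = 0.682 | 30/44 = 0.682 |
| 28 | 0.682 × 1/2 = 0.341 | 0.682 × 29/30 = 0.659 |
| 33 | 0.341 × 0/1 = 0 | 0.659 × 28/29 = 0.636 |

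Under the stated rule the first late death takes the curve through 0.5, so a median would be reported at month 28. With the same patients kept at risk, the median is not reached.

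**Chance that the effect is triggered.** It takes one event after the last scan. With m patients event-free at month 24 and annual risk q (assumed; the documents give no rate), the probability is 1 − (1 − q)^m:
- q = 2%: 33%, 46% and 55% for m = 20, 30 and 40.
- q = 5%: 64%, 79% and 87%.

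**Simulation.** Inputs: 46 responders (75% of 62 is 46.5); scans at months 2, 6, 12 and 24, each ±14 days; events counted to month 36; constant hazard with half the events deaths (assumed); 600 runs per setting. No event-free patient remained at risk after the month-24 scan window in any run.

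| Annual hazard | Mean month-36 estimate, last-scan censoring | Mean, status verified to month 36 | True value | Runs reaching exactly 0 |
|---|---|---|---|---|
| 0.05 | 0.12 | 0.86 | 0.86 | 86% |
| 0.10 | 0.02 | 0.74 | 0.74 | 97% |
| 0.20 | 0.001 | 0.55 | 0.55 | 99.7% |
| 0.40 | 0.00 | 0.30 | 0.30 | 100% |

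In runs without a late event the last value was carried to month 36, which is why the first mean is above zero.

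**Where the last scan falls on each clock.** Month 24 is counted from the end of treatment. With a 14-day gap before cycle 2, treatment spans 28 + 14 + 28 = 70 days (CR path) or 28 + 14 + 84 = 126 days (PR path), which is 2.3 or 4.1 months at 30.4 days per month. On the PFS clock, from first dose, the last scan is therefore at about 26 or 28 months, ±14 days. The DOR clock starts at documented response. If that is the day-42 scan of Section 11.1.2, the last scan is 28 to 84 days later than month 24, or about 25 to 27 months. If it is the scan 8 weeks after treatment, the last scan is at about 24 − 1.8 = 22 months. The risk set therefore empties over a few months and not at one instant.

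**The case against.** - **PFS may not be affected.** Section 12.1.5 names the last assessment without saying of what. The word tumor appears only in the fallback clause, and Section 12.1.6 uses the same phrase for OS, where it cannot mean a scan. If the month-36 status visit counts, the PFS problem disappears. This stands: a reader might infer that both endpoints are certainly at fault, but the text establishes that only for DOR.
- **Section 14.5 leaves death out of DOR.** Under it, the two deaths in the illustration would not be DOR events. That also stands, as a contradiction to resolve. It does not remove the fault, because a progression confirmed after the last scan has the same effect.
- **The effect is conditional and the rates are assumed.** True. With no event after the last scan, the curve simply ends there. Unscheduled scans in event-free patients would soften the fall, but the plan provides for none.
- **Censoring at the last progression-free assessment is conventional.** It is, and it works when assessments continue as long as events are counted. Here they stop a year sooner.
- **The endpoints are secondary and descriptive.** No success rule, futility rule or sample size depends on them, and the plan commits to no median or 36-month landmark. Numbers at risk printed under the curve would show how thin the tail is, but would not correct the estimate.

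**Conclusion.** For DOR as defined in Section 12.1.4, the event window and the censoring window do not match. After the last scheduled scan the curve is not a valid estimate if any event occurs there: it falls artificially, reaches zero at the last late event in the absence of unscheduled scans, and can yield a false median. In the illustration the month-33 value is 0 where 0.636 is right. For PFS the same holds only if the censoring assessment is a tumor assessment; the fallback clause points that way but the wording is ambiguous.

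A reader might go further and conclude that both curves are bound to collapse at month 24, or that the trial's efficacy result is compromised. The documents support neither. The fall needs at least one late event. The last scan is fixed relative to end of treatment, not at month 24 on either endpoint's clock. Estimates up to that scan and the primary ORR are unaffected. The sizes given here rest on assumed event counts and hazards.

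**What to change.** In Sections 12.1.4 and 12.1.5, make the two windows match by one of these rules:

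1. Censor event-free patients at the last visit with recorded progression-free disease status, through month 36.
2. End DOR and PFS for each patient at the scan visit scheduled 24 months after treatment (about 26 to 28 months from first dose on the PFS clock). List later deaths and progressions descriptively; deaths still count in OS.

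With either rule, state in Section 12.1.5 which assessment sets the PFS censoring date, and reconcile the DOR event in Section 14.5 with Section 12.1.4 by saying whether death counts.

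The cost is mainly wording, with no added scans, visits or patients. Rule 1 relies on clinical status, possibly from a virtual visit, where there is no imaging after month 24. Rule 2 truncates both endpoints and removes a few late events from them. The choice should be made before late events are seen, so that it does not look outcome-driven.

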12.1.5 Progression Free Survival

Progression free survival (PFS) is defined as the time from first dose to documented disease progression, or death from any cause, whichever occurs first. Data for subjects who are still alive and free from progression at the time of data cutoff date, lost to follow-up, have discontinued the study, or have initiated NPT will be censored on last assessment (or, if no post-baseline tumor assessment, at the time of first dose plus 1 day).

12.1.6 Overall Survival

Overall survival (OS) is defined as the time from first dose to death from any cause. Data for subjects who are still alive at the time of data cutoff date, lost to follow-up, have discontinued the study (or, if no post-baseline assessment, at the time of first dose plus 1 day) will be censored on last assessment.

12.1.7 Time to Treatment Failure

Time to treatment failure (event-free survival) is measured from the time from study entry to any treatment failure including discontinuation of treatment for any reason, such as disease progression, toxicity, patient preference, initiation of new treatment without documented progression, or death. This composite endpoint is generally not encouraged by regulatory agencies because it combines efficacy, toxicity and patient withdrawal.

13.0 DATA REPORTING / REGULATORY CONSIDERATIONS

Adverse event lists, guidelines, and instructions for AE reporting can be found in Section 8.0 (Adverse Events: List and Reporting Requirements).

13.1 Data Reporting

The Adverra EDC™ and OnCore™ databases will be utilized, as required by the Case Comprehensive Cancer Center and Cleveland Clinic, to provide data collection for both accrual entry and trial data management. Adverra EDC and OnCore™ are Clinical Trials Management Systems housed on secure servers. Access to data through Adverra EDC and OnCore™ is restricted by user accounts and assigned roles. Once logged into the Adverra EDC or OnCore™ system with a user ID and password, Adverra EDC™ and OnCore™ define roles for each user which limits access to appropriate data. User information and password can be obtained by contacting the OnCore™ Administrator at [contact] for OnCore™ access, and [contact] for Adverra EDC™ access.

Adverra EDC™ is designed with the capability for study setup, activation, tracking, reporting, data monitoring and review, and eligibility verification. When properly utilized, Adverra EDC™ is 21 CFR 11 compliant. This study will utilize electronic Case Report Form completion in the Adverra EDC™ database. A calendar of events and required forms are available in Adverra EDC™.

13.2 Regulatory Considerations

The study will be conducted in compliance with ICH guidelines and with all applicable federal (including 21 CFR parts 56 & 50), state or local laws.

13.2.1 Written Informed consent

Provision of written informed consent must be obtained prior to any study-related procedures. The Principal Investigator will ensure that the subject is given full and adequate oral and written information about the nature, purpose, possible risks and benefits of the study as well as the subject's financial responsibility. Subjects must also be notified that they are free to discontinue

from the study at any time. The subject should be given the opportunity to ask questions and be allowed time to consider the information provided.

The original, signed written Informed Consent Form must be kept with the Research Chart in conformance with the institution's standard operating procedures. A copy of the signed written Informed Consent Form must be given to the subject. Additionally, documentation of the consenting process should be located in the research chart.

13.2.2 Subject Data Protection

In accordance with the Health Information Portability and Accountability Act (HIPAA), a subject must sign an authorization to release medical information to the sponsor and/or allow the sponsor, a regulatory authority, or Institutional Review Board access to subject's medical information that includes all hospital records relevant to the study, including subjects' medical history.

13.2.3 Retention of records

The Principal Investigator of The Case Comprehensive Cancer Center supervises the retention of all documentation of adverse events, records of study drug receipt and dispensation, and all IRB correspondence for as long as needed to comply with local, national and international regulations. No records will be destroyed until the Principal Investigator confirms destruction is permitted.

13.2.4 Audits and inspections

Authorized representatives of the sponsor, a regulatory authority, an Independent Ethics Committee (IEC) or an Institutional Review Board (IRB) may visit the site to perform audits or inspections, including source data verification. The purpose of an audit or inspection is to systematically and independently examine all study-related activities and documents to determine whether these activities were conducted, and data were recorded, analysed, and accurately reported according to the protocol, Good Clinical Practice (GCP), guidelines of the International Conference on Harmonization (ICH), and any applicable regulatory requirements. For multi-center studies, participating sites must inform the sponsor-investigator of pending audits.

